11.10.1. Analysis of HRQOL, lung capacity

The analysis will be performed on the TVC.

Descriptive statistics (median, mean, range, standard deviation, first and third quartiles) on the **EXACT-PRO, CAT, SGRQ-C** scores, on **FEV₁% of predicted normal value** will be tabulated by specified visit.

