2.3. Tertiary objectives

- To evaluate the effect of the investigational vaccine on the presence, *acquisition/apparition* and load of NTHi and/or Mcat at stable visits and AECOPD by PCR. **(Amended 27 March 2019)**
- To evaluate the effect of the investigational vaccine on the presence, *acquisition/apparition* and load of NTHi and/or Mcat at stable visits and AECOPD in a subset of sputum samples by culture. **(Amended 27 March 2019)**
- To explore the efficacy of the investigational vaccine as compared to placebo with respect to the rate of all AECOPDs and by severity (i.e. mild, moderate or severe) associated with NTHi and/or Mcat detected in a subset of sputum samples by culture.
- To explore the impact of the investigational vaccine on health-related quality of life (HRQOL).
- To explore the impact of the investigational vaccine on use of medication for COPD and Healthcare Resource Utilisation.
- To explore the impact of the investigational vaccine on lung function.
- To describe selected biomarkers in stable COPD and during AECOPD.
- To explore the T helper profile of the PD-, PE-, PilA-, UspA2-specific CD4⁺/ CD8⁺ T cell responses.
- To collect blood and sputum samples for assay development, for lung microbiome analysis, to explore the level of inflammation (into the lung) and/ or for additional evaluation of the immune responses to the investigational vaccine and to other potential pathogens involved in AECOPD.
- To explore the data for an immune correlate of protection.

Refer to Section 11.3 for the definition of the tertiary endpoints and to section 11.12.1 for the reporting of tertiary endpoint results.

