- **HRQOL assessments:**
 - All subjects will be asked to complete the **COPD assessment test (CAT)** at the Screening Visit (pre-Day 1), Visit 6 (Day 271), Visit 8 (Day 451) and at each AECOPD visit from first vaccination to study conclusion.
 - All subjects will be asked to complete **St. George's Respiratory Questionnaire for COPD patients (SGRQ-C)** at the Screening Visit (pre-Day 1), Visit 6 (Day 271), at Visit 8 (Day 451) and at each AECOPD visit from first vaccination to study conclusion.
- **Pre- and post-bronchodilator spirometry assessments** will be done for all subjects at the Screening Visit (pre-Day 1), Visit 6 (Day 271) and at Visit 8 (Day 451).
- Type of study: self-contained
- Data collection: Electronic Case Report Form (eCRF), electronic Diary Cards (eDiary) and Phone Contacts.
- Safety monitoring: Safety evaluations by the safety review team (SRT) (blinded) and by an internal Safety Review Committee (iSRC) (unblinded) will be performed.

Refer to section 9.10 for detailed description of safety monitoring.

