11.3. Tertiary endpoints**Sputum sample PCR:**

- Occurrence (presence and absence), ***acquisition, apparition***, and bacterial load measured by PCR of NTHi and/or Mcat in sputum before first vaccination and at Day 91, Day 181, Day 271, Day 361 and Day 451 and at each AECOPD visit.
(Amended 27 March 2019)

Sputum sample culture:

- Occurrence (presence and absence), ***acquisition, apparition***, and semi-quantitative bacterial load measured in a subset of sputum sample by culture of NTHi and/or Mcat in sputum before first vaccination and at Day 91, Day 181, Day 271, Day 361 and Day 451 and at each AECOPD visit. **(Amended 27 March 2019)**
- Rate of NTHi-associated and Mcat-associated, moderate and severe AECOPD.
- Rate of NTHi-associated and Mcat-associated any severity AECOPD.

- Rate of NTHi-associated and Mcat-associated AECOPD, by severity.
- Time to first moderate or severe NTHi-associated and/or Mcat-associated AECOPD.
- Time to first any NTHi-associated and rate Mcat-associated AECOPD.
- Time to first NTHi-associated and rate Mcat-associated AECOPD, by severity.
- Duration of each moderate and severe NTHi-associated and Mcat-associated AECOPD.
- Duration of NTHi-associated and/or Mcat-associated AECOPDs of any severity.
- Duration of NTHi-associated and/or Mcat-associated AECOPD, by severity.

QOL:

- Assessment of EXACT-PRO score, daily in the evening throughout the study, in all subjects.
- Assessment of CAT score at Screening, Day 271 and Day 451, and from first vaccination to study conclusion for each AECOPD visit, in all subjects.
- Assessment of SGRQ-C score at Screening, Day 271 and Day 451, and from first vaccination to study conclusion for each AECOPD visit, in all subjects.
- Assessment of use of medication to treat (AE)COPD and healthcare utilization in all subjects throughout the study period.

Lung function:

- Assessment of FEV1% of predicted normal value at Screening, Day 271 and Day 451, in all subjects.

Biomarkers:

- Concentration of selected biomarkers (fibrinogen, hsCRP and IP-10), at Day 1 and Day 451, and for each AECOPD visit from first vaccination to study conclusion.

CMI:

- T helper profile of the specific CD4⁺ (CD8⁺) T cell response based on the expression of T helper 1, T helper 2 and T helper 17 specific markers at Day 1, Day 91, Day 271 and Day 451.

Assay development, microbiome analysis and lung inflammation:

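### CAT, SGRQ-C and FEV1% predicted get only descriptive tables by visit, with no vaccine-minus-placebo estimate and no use of the Screening value as a baseline

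*Protocol*

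**What the plan says.** Section 11.10.1 is the protocol's whole analysis text for these measures. It works on the total vaccinated cohort and specifies "Descriptive statistics (median, mean, range, standard deviation, first and third quartiles) on the" EXACT-PRO, CAT and SGRQ-C scores and FEV1% predicted, which "will be tabulated by specified visit". It does not mention a split by group, a change from Screening, a between-group difference, an interval or a model.

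The matching tertiary objectives in Section 2.3 are worded as questions about the vaccine. One is "To explore the impact of the investigational vaccine on lung function"; a parallel objective asks the same for health-related quality of life.

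Section 11.3 lists the timepoints: "Assessment of CAT score at Screening, Day 271 and Day 451", "Assessment of SGRQ-C score at Screening, Day 271 and Day 451" and "Assessment of FEV1% of predicted normal value at Screening, Day 271 and Day 451, in all subjects". CAT and SGRQ-C are also taken at AECOPD visits. EXACT-PRO is different: it is a diary score collected every evening, and no Screening-visit value is listed for it.

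Section 11.11 adds that comparisons serving secondary and tertiary objectives are descriptive and need cautious reading.

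**The concern.** The impact of a vaccine on a score is a contrast between vaccine and placebo. A table of summaries at each visit supplies the raw material for that contrast but does not state it, and Section 11.10.1 does not say that the tables are split by group. Followed as written, the section gives these two objectives no effect estimate and no interval.

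The second part is precision. Questionnaire scores and FEV1 usually differ more between patients than they move within a patient over a year. A Screening value measured on every subject can remove part of that between-patient spread from a group comparison. The section gives it no such role. What is at stake is the width of the interval on tertiary endpoints, and having the form of the comparison fixed before the data are seen, so that nobody later chooses among raw, change-from-Screening and adjusted versions.

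**Working it through.** The protocol states no figure for this analysis, so there is none to reproduce. The check sets sections side by side and then sizes the precision at issue.

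**What the protocol does for comparable endpoints**

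- Section 11.8, acquisition and apparition (tertiary): percentages by treatment group plus a risk ratio between the groups.
- Section 11.9.2, antibody concentrations (called exploratory): an ANCOVA with group, age category, GOLD grade and country, the pre-Dose 1 value as covariate, and a 95% CI for the ratio.
- Section 11.9.3, cell-mediated response: descriptive statistics, stated for each group.
- Section 11.9.4, biomarkers: descriptive statistics only. Here the objective in Section 2.3 is merely to describe, so method and objective match.
- Section 11.10.1, quality of life and lung function: descriptive statistics only, with an objective about impact. Method and objective do not match.

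**Size of the precision loss**

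Inputs:

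- About 300 subjects per group (Section 3).
- 85% expected to complete the one-year follow-up (Section 11.4), so n = 300 × 0.85 = 255 per group.
- Correlation r between the Screening and Day 451 values: not in the document. It is an assumption, shown over 0.3 to 0.9.
- Results are in units of the outcome's standard deviation, because the document gives no SD for any of these measures. Equal SDs at both times and in both groups are assumed.

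Standard errors of the between-group difference:

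- Day 451 values alone: √(2/n)
- Change from Screening: √(4(1 − r)/n)
- ANCOVA with Screening as covariate: √(2(1 − r²)/n)

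The 95% CI half-width is 1.96 times the standard error. For Day 451 alone: 1.96 × √(2/255) = 0.174 SD, whatever r is.

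| r (assumed) | ANCOVA variance ÷ Day 451-only variance (1 − r²) | ANCOVA half-width (SD) | Change-score half-width (SD) |
|---|---|---|---|
| 0.3 | 0.91 | 0.166 | 0.205 |
| 0.5 | 0.75 | 0.150 | 0.174 |
| 0.7 | 0.51 | 0.124 | 0.134 |
| 0.8 | 0.36 | 0.104 | 0.110 |
| 0.9 | 0.19 | 0.076 | 0.078 |

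For r from 0.5 to 0.8 the variance falls by r², that is by 25% to 64%. At r = 0.7 the standard error falls by 1 − √0.51 = 0.29, or about 29%. A simple change from Screening is worse than using Day 451 alone when r is below 0.5, so the covariate form is the safer choice.

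**The case against.** The strongest reply is that nothing here is false. The objectives are tertiary and exploratory, Section 11.11 expects descriptive comparisons, and models for tertiary questionnaires and spirometry are commonly left to the statistical analysis plan, which Section 6.2.2.2.1 mentions and which is not at hand. The parent Section 11.10 tabulates solicited events by group, so group columns may be intended here too. The precision figures rest on an assumed correlation; at 0.3 the variance gain is only 9%.

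Much of this stands, and it sets the priority. It does not remove the point. Section 11.10.1 is not silent; it names a method, and that method stops short of its objective. Section 11.12 asks that departures from the protocol's outlined analysis be justified in the report. Section 11.11 governs how a comparison is read; it does not supply one.

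Three stronger readings are tempting, and the protocol does not support them:

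- *The Screening values go unused.* They do not. Screening is a listed timepoint, so the values will be tabulated. Screening spirometry also establishes eligibility and GOLD grade, which is a minimisation factor and a covariate in the primary model. The values are only not used as a baseline for these endpoints.
- *The objectives cannot be answered, or an effect would be buried.* Two randomised groups of about 255 can be compared on follow-up values with a half-width of about 0.174 SD. That is less precise, but it is an answer, provided the tables are by group.
- *EXACT-PRO has the same fault.* It has no Screening-visit score, so the baseline argument does not apply to it.

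**Conclusion.** The point holds as a low-priority improvement. Section 11.10.1 gives CAT, SGRQ-C and FEV1% predicted no between-group estimate or interval and does not use Screening as a baseline, while the objectives ask about vaccine impact and the protocol states such contrasts for other exploratory endpoints.

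The cost is a 95% CI half-width of about 0.174 SD where 0.150 to 0.104 SD would be available at correlations of 0.5 to 0.8. This rests on the assumed correlations, on 255 subjects per group having both values, and on equal SDs. The comparator is the unadjusted Day 451 contrast that a reader could form from group tables; the protocol does not itself plan one. If the statistical analysis plan already contains an adjusted contrast, what remains is to align the protocol text with it.

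**What to change.** Amend Section 11.10.1 in two ways:

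- State that the descriptive tables are by group and visit.
- For CAT, SGRQ-C total and FEV1% predicted, add the vaccine-minus-placebo difference with 95% CI at Day 271 and Day 451. Take it from an ANCOVA or repeated-measures model with the Screening value and the four minimisation factors (age group, number of moderate or severe exacerbations in the previous year, GOLD grade, country) as covariates. Label the results exploratory and descriptive, in line with Section 11.11.

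The cost is one model per measure on data already collected. The small downside is a few more exploratory estimates to be read with restraint. The wording should be settled before unblinding.

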11.11. Interpretation of analyses

The primary objective of this POC will be evaluated at alpha error of 13% (two-sided test) which is the measurement of the accuracy of our estimation.

Comparative analyses related to the secondary and tertiary objectives, with the aim to characterise the difference in reactogenicity/ immunogenicity/ efficacy between groups will be descriptive and should be interpreted with caution.

11.12. Conduct of analyses

Any deviation(s) or change(s) from the original statistical plan outlined in this protocol will be described and justified in the final study report.

11.12.1. Sequence of analyses

The analyses of the primary, secondary and tertiary endpoints will be completed once data are released. They will be finalized at the end of the trial, when all data up to and including Visit 8 (Day 451) will be available and cleaned.

An integrated clinical study report containing all data will be written and made available to the investigators.

If the data for tertiary endpoints become available at a later stage, (an) additional analysis/ analyses will be performed. These data will be documented in annex(es) to the study report and will be made available to the investigators at that time.

12. ADMINISTRATIVE MATTERS

To comply with ICH GCP administrative obligations relating to data collection, monitoring, archiving data, audits, confidentiality, public disclosure requirements and publications must be fulfilled.

12.1. Case Report Form/electronic Case Report Form instructions

A validated GSK defined electronic data collection tool will be used as the method for data collection.

In all cases, subject initials will not be collected nor transmitted to GSK. Subject data necessary for analysis and reporting will be entered/transmitted into a validated database or data system. Clinical data management will be performed in accordance with applicable GSK standards and data cleaning procedures.

While completed eCRFs are reviewed by a GSK Biologicals' Site Monitor at the study site, omissions or inconsistencies detected by subsequent eCRF review may necessitate clarification or correction by the investigator or appropriately qualified designee. In all cases, the investigator remains accountable for the study data.

The investigator will be provided with a CD-ROM of the final version of the data generated at the investigational site once the database is archived and the study report is complete and approved by all parties.

12.2. Study Monitoring by GSK Biologicals

GSK will monitor the study to verify that, amongst other items, the:

- Data are authentic, accurate, and complete.
- Safety and rights of subjects are being protected.
- Study is conducted in accordance with the currently approved protocol, any other study agreements, GCP and all applicable regulatory requirements.

The investigator and the head of the medical institution (where applicable) agrees to allow the monitor direct access to all relevant documents.

The investigator must ensure provision of reasonable time, space and qualified personnel for monitoring visits.

Direct access to all study-site related and source data is mandatory for the purpose of monitoring review. The monitor will perform an eCRF review and a Source Document Verification (SDV). By SDV we understand verifying eCRF entries by comparing them with the source data that will be made available by the investigator for this purpose.

The Source Documentation Agreement Form describes the source data for the different data in the eCRF. This document should be completed and signed by the site monitor and investigator and should be filed in the investigator's study file. Any data item for which the eCRF will serve as the source must be identified, agreed and documented in the source documentation agreement form.

Upon completion or premature discontinuation of the study, the monitor will conduct site closure activities with the investigator or site staff, as appropriate, in accordance with applicable regulations, GCP, and GSK procedures.

12.3. Record retention

Following closure of the study, the investigator must maintain all site study records (except for those required by local regulations to be maintained elsewhere) in a safe and secure location. The records must be easily accessible, when needed (e.g. audit or inspection), and must be available for review in conjunction with assessment of the facility, supporting systems, and staff. Where permitted by applicable laws/regulations or institutional policy, some or all of these records can be maintained in a validated format other than hard copy (e.g. microfiche, scanned, electronic); however, caution needs to be exercised before such action is taken. The investigator must ensure that all reproductions are legible and are a true and accurate copy of the original and meet accessibility and retrieval standards, including re-generating a hard copy, if required. Furthermore, the

investigator must ensure that an acceptable back-up of the reproductions exists and that there is an acceptable quality control procedure in place for making these reproductions.

GSK will inform the investigator/institution of the time period for retaining these records to comply with all applicable regulatory requirements. The minimum retention time will meet the strictest standard applicable to a particular site, as dictated by ICH GCP, any institutional requirements, applicable laws or regulations, or GSK standards/procedures, otherwise, the minimum retention period will default to 25 years after completion of the study report.

The investigator/institution must notify GSK of any changes in the archival arrangements, including, but not limited to archival at an off-site facility, transfer of ownership of the records in the event the investigator leaves the site.

12.4. Quality assurance

To ensure compliance with GCP and all applicable regulatory requirements, GSK may conduct a quality assurance audit. Regulatory agencies may also conduct a regulatory inspection of this study. Such audits/inspections can occur at any time during or after completion of the study. If an audit or inspection occurs, the investigator and institution agree to allow the auditor/inspector direct access to all relevant documents and to allocate his/her time and the time of his/her staff to the auditor/inspector to discuss findings and any relevant issues.

12.5. Posting of information on publicly available clinical trial registers and publication policy

GSK assures that the key design elements of this protocol will be posted on the GSK website and in publicly accessible database(s) such as clinicaltrials.gov, in compliance with the current regulations.

GSK also assures that results of this study will be posted on the GSK website and in publicly accessible regulatory registry(ies) within the required time-frame, in compliance with the current regulations. The minimal requirement is to have primary endpoint summary results disclosed at latest 12 months post primary completion date (PCD) and to have secondary endpoint disclosed at latest 12 months after the last subject last visit (LSLV) as described in the protocol.

As per EU regulation, summaries of the results of GSK interventional studies (phase I-IV) in adult population conducted in at least one EU member state will be posted on publicly available EMA registers within 12 months of EoS (as defined in the protocol) in the concerned EU member state. However, where, for scientific reasons detailed in the protocol, it is not possible to submit a summary of the results within one year in the concerned EU member state, the summary of results shall be submitted as soon as it is available. In this case, the protocol shall specify when the results are going to be submitted, together with a justification.

GSK also aims to publish the results of these studies in searchable, peer reviewed scientific literature and follows the guidance from the International Committee of Medical Journal Editors.

12.6. Provision of study results to investigators

Where required by applicable regulatory requirements, an investigator signatory will be identified for the approval of the study report. The investigator will be provided reasonable access to statistical tables, figures, and relevant reports and will have the opportunity to review the complete study results at a GSK site or other mutually-agreeable location.

GSK Biologicals will also provide the investigator with the full summary of the study results. The investigator is encouraged to share the summary results with the study subjects, as appropriate.

12.7. Data Sharing

Under the framework of the SHARE initiative, results of GSK studies may be combined with non- GSK studies, to investigate further about the study product(s) and other product(s), and /or the disease/condition under investigation and related diseases and conditions.

13. COUNTRY SPECIFIC REQUIREMENTS

13.1. Requirements for Germany

Explanatory statement concerning Gender Distribution (Article 7, paragraph 2 (12) of the German GCP ORDER)

For this NTHI MCAT-002 study, there is no intention to conduct specific analyses investigating the relationship between gender and the safety and efficacy of the investigational NTHi-Mcat vaccine. Recruitment will include males and females. To not expose pregnant women and their foetuses/children to an early-phase investigational vaccine, females enrolled in this trial will either be of non-childbearing potential (i.e., have a current tubal ligation or occlusion, hysterectomy, bilateral ovariectomy or be premenarchal or postmenopausal), or if she is of childbearing potential, she must practice adequate contraception for 30 days prior to the beginning of the administration of study treatment, have a negative pregnancy test and continue such precautions during the entire study treatment period and for 2 months after completion of the injection series (Refer to the study protocol, Section 5.2 “Inclusion criteria” and Section 5.3 “Exclusion criteria”). The recruitment will be closed to females who are pregnant or lactating. Similarly, patients becoming or deciding to become pregnant during the study must stop the study treatment administrations.

Historically, COPD was considered a disease of males. The past few decades have seen a shift in this paradigm. In the United States, between the periods of the First National

Health and Nutrition Examination Survey (NHANES I) and NHANES III, the prevalence of spirometrically determined moderate COPD increased in women from 50.8 per 1000 to 58.2 per 1000, whereas the prevalence decreased in men from 108.1 per 1000 to 74.3 per 1000.3 Data from the National Health Interview Survey show that the self-reported prevalence of COPD in the United States was stable from 1998 through 2009 and has remained higher in women than in men. A similar trend is seen in other developed countries such as Canada, the Netherlands, and Australia [Aryal, 2013]. There are no reports of gender differences in the efficacy or safety outcomes for patients receiving the investigational NTHi-Mcat vaccine.

